15.8.3 Type I Error Rates for Safety (Non-inferiority)

Table 10 displays the type I error rates for the primary safety non-inferiority test under every combination of enrollment rate (slow, expected, fast), control CSE rate Q_C (0.07, 0.08, 0.10), and data generation hazard (Methods Saf_1 and Saf_2). Also displayed is the average achieved sample size. Each of these scenarios is for the case that $Q_T = Q_C + 0.08$ and assumes that the effectiveness sample size assessments would always stop enrolling for promise and the final effectiveness analysis would always end by demonstrating non-inferiority. Each of the 18 scenarios is the result of running 10,000 simulated clinical trials. Among the 18 estimated type I error rates, the mean value is 0.0453, and the max is 0.0540. No values exceed the range of what is expected in a simulation of 10,000 iterations, calculated as a 95% probability interval $0.05 \pm 1.96 \times \sqrt{(0.05 \times 0.95 / 10,000)} = 0.05 \pm 0.0043$, with upper bound 0.0543.

Table 10 Type I Error Rates for Primary Safety Non-inferiority Test as Data Generation Parameters Vary (Effectiveness data always indicate sample size stop)

Data Generation		Type I Error Rates (as accrual varies)			Average Sample Size (as accrual varies)		
Method	Q_C	Slow	Expected	Fast	Slow	Expected	Fast
Saf_1	0.100	0.0539	0.0491	0.0429	447	455	467
Saf_1	0.080	0.0507	0.0528	0.0442	449	457	465
Saf_1	0.060	0.0540	0.0515	0.0486	448	456	469
Saf_2	0.100	0.0407	0.0412	0.0378	468	475	498
Saf_2	0.080	0.0433	0.0414	0.0427	463	476	498
Saf_2	0.060	0.0438	0.0385	0.0379	465	475	495

All estimates are based on 10,000 simulated trials (per scenario).

The results in **Table 10** are computed under the assumption that the primary effectiveness objective results are so strongly favorable that the effectiveness portion of the sample size assessments would always indicate a stop for promising trend. **Table 11** presents results when this assumption is altered so that the sample size is jointly determined by trends in both the primary safety and effectiveness endpoints, as described in Section 12, and primary effectiveness data are generated under the expected effectiveness assumptions that $P_T = P_C = 0.650$ and Method Eff_1 . Conservatively, it is further assumed that the effectiveness endpoint would always pass its non-inferiority criterion once follow-up is complete, even though this will not always be the case.

**Table 11 Type I Error Rates for Primary Safety Non-inferiority Test as Data Generation Parameters Vary
(Effectiveness data generated using $P_T = P_C = 0.65$, Method Eff_1)**

Data Generation		Type I Error Rates (as accrual varies)			Average Sample Size (as accrual varies)		
Method	Qc	Slow	Expected	Fast	Slow	Expected	Fast
Saf_1	0.100	0.0500	0.0479	0.0405	451	460	470
Saf_1	0.080	0.0473	0.0449	0.0454	453	458	470
Saf_1	0.060	0.0484	0.0446	0.0418	451	456	470
Saf_2	0.100	0.0406	0.0405	0.0364	465	477	498
Saf_2	0.080	0.0401	0.0376	0.0337	451	460	470
Saf_2	0.060	0.0413	0.0333	0.0341	453	458	470

All estimates are based on 10,000 simulated trials (per scenario).

Each of the 18 estimated Type I error rates in **Table 11** is the result of running 10,000 simulated clinical trials. Among the 18 estimated type I error rates, the mean value is 0.0416, and the max is 0.0500. No values exceed the range of what is expected in a simulation of 10,000 iterations, calculated as a 95% probability interval $0.05 \pm 1.96 \times \sqrt{(0.05 \times 0.95 / 10000)} = 0.05 \pm 0.0043$, with upper bound 0.0543.

Although **Table 10** and **Table 11** generate data with varying methods, the method applied for the Treatment Group is the same as that applied for the Control Group. The below **Table 12** presents a study of safety type I error rates when the Treatment and Control groups are generated with different methods. Specifically, 4 null scenarios of 10,000 iterations each were conducted, systematically and separately varying data generations methods $\{Saf_1, Saf_2\}$ in the Treatment group and $\{Saf_1, Saf_2\}$ in the Control group, under the assumption of 16% success rate in the Treatment group and 8% success rate in the Control group. Effectiveness data in these scenarios were generated using method Eff_1 for both treatment groups, with the expected success rate of 65% in each group.

As in Table 8, the sample size is jointly determined by trends in both the primary safety and effectiveness endpoints, but it is conservatively assumed that the effectiveness endpoint would always pass its non-inferiority criterion once follow-up is complete, even though this will not always be the case. Enrollment followed the Expected rate, as described in Section 15.7.

**Table 12 Type I Error Rates for Safety Non-Inferiority as data generation methods vary,
(when $Q_T = 0.08+0.08$, $Q_C = 0.08$)**

Data Generation Method	Control Group	
	Treatment Group	Saf1
Saf1	0.0449	0.0463
Saf2	0.0380	0.0376

All estimates are based on 10,000 simulated trials (per scenario).

In **Table 12**, the maximum value is 0.0463. In **Table 12** (as well as **Table 10** and **Table 11**), no estimated type I error rates exceed the range of what is expected in a simulation of 10,000 iterations, calculated as a 95% probability interval $0.05 \pm 1.96 \times \sqrt{(0.05 \times 0.95 / 10000)} = 0.05 \pm 0.0043$, with upper bound 0.0543. Therefore, the type I error rate of the safety test is considered controlled at the level 0.05.

15.8.4 Type I Error Rates for Effectiveness (Superiority)

As described in Sections 6 and 9.2, superiority for the primary effectiveness endpoint will be tested as a secondary objective. The methods are identical to those for the primary effectiveness non-inferiority test (Sections 9.1 and 13.1) except that (1) there is no non-inferiority margin, and (2) the one-sided type I error

rate is set at the level 0.025. Superiority is considered established if the posterior probability $\Pr(P_T > P_C | \text{data}) > \Psi_{\text{eff, sup}} = 0.977$ at the final analysis.

Table 13 displays the estimated Type I error rates under every combination of enrollment rate (slow, expected, fast), control success rate P_C (0.60, 0.65, 0.70), and data generation hazard (Methods Eff_1 , Eff_2 , and Eff_3). Each of these scenarios is for the case that $P_T = P_C$ and assumes that the safety sample size assessments would always stop enrolling for promise and the final safety analysis would always end by demonstrating non-inferiority. Furthermore, enrollment stopping is based on the predictive probabilities of demonstrating non-inferiority for this effectiveness endpoint (as specified in Section 12), without regard for any predictive probabilities of demonstrating superiority. Nevertheless, superiority is tested at the final analysis (12 months after enrollment stops).

Each of the 27 scenarios is the result of running 10000 simulated clinical trials. Among the 27 estimated type I error rates, the mean value is 0.0242, and the max is 0.0277. No values exceed the upper bound of what is expected in a simulation of 10,000 iterations, calculated as a 95% probability interval $0.025 \pm 1.96 \times \sqrt{0.025 \times 0.0975 / 10000} = 0.025 \pm 0.0031 = (0.0219, 0.0281)$.

Table 13 Type I Error Rates for Primary Effectiveness Superiority Test as Data Generation Parameters Vary (Safety data always indicate sample size stop)

Data Generation		Type I Error Rates (as accrual varies)		
Method	$P_C = P_T$	Slow	Expected	Fast
Eff_1	0.600	0.0226	0.0227	0.0277
	0.650	0.0221	0.0255	0.0248
	0.700	0.0232	0.0247	0.0258
Eff_2	0.600	0.0238	0.0238	0.0245
	0.650	0.0234	0.0274	0.0250
	0.700	0.0224	0.0238	0.0243
Eff_3	0.600	0.0259	0.0245	0.0229
	0.650	0.0239	0.0239	0.0245
	0.700	0.0222	0.0223	0.0258

All estimates are based on 10,000 simulated trials (per scenario).

The results in **Table 13** are computed under the assumption that the primary safety objective results are so strongly favorable that the safety portion of the sample size assessments would always indicate a stop for promising trend, and the primary safety hypothesis test would always pass its non-inferiority criterion.

Table 14 presents results when this assumption is altered so that the sample size is jointly determined by trends in both the primary safety and effectiveness endpoints, as described in Section 12, and primary safety data are generated under the expected safety assumptions that $Q_T = Q_C = 0.080$ and Method Saf_1 . Conservatively, it is further assumed that the safety endpoint would always pass its non-inferiority criterion once follow-up is complete, even though this will not always be the case.

**Table 14 Type I Error Rates for Primary Effectiveness Superiority Test as Data Generation Parameters Vary
(Safety data generated using $Q_T = Q_C = 0.080$, Method Saf_1)**

Data Generation		Type I Error Rates (as accrual varies)		
Method	$P_C = P_T$	Slow	Expected	Fast
Eff_1	0.600	0.0215	0.0230	0.0265
Eff_1	0.650	0.0221	0.0254	0.0238
Eff_1	0.700	0.0219	0.0248	0.0244
Eff_2	0.600	0.0245	0.0243	0.0227
Eff_2	0.650	0.0211	0.0224	0.0232
Eff_2	0.700	0.0240	0.0237	0.0263
Eff_3	0.600	0.0239	0.0238	0.0228
Eff_3	0.650	0.0225	0.0268	0.0253
Eff_3	0.700	0.0232	0.0234	0.0235

All estimates are based on 10,000 simulated trials (per scenario).

Each of the 27 estimated Type I error rates in **Table 14** is the result of running 10,000 simulated clinical trials. Among the 27 estimated type I error rates, the mean value is 0.0237, and the max is 0.0268. No values exceed the range of what is expected in a simulation of 10,000 iterations, calculated as a 95% probability interval $0.025 \pm 1.96 \times \sqrt{(0.025 \times 0.975 / 10000)} = 0.025 \pm 0.0031$, with upper bound 0.0281.

Although **Table 13** and **Table 14** generate data with varying methods, the method applied for the Treatment Group is the same as that applied for the Control Group. The below **Table 15** presents a study of type I error rates for the secondary superiority objective when the Treatment and Control groups are generated with different methods. Specifically, 9 null scenarios of 10,000 iterations each were conducted, systematically and separately varying data generation methods $\{Eff_1, Eff_2, Eff_3\}$ in the Treatment group and $\{Eff_1, Eff_2, Eff_3\}$ in the Control group, under the superiority null assumption of 65% success rate in each treatment group. Safety data in these scenarios were generated using method Saf_1 for both treatment groups, with expected rates of 8% in each group. As in **Table 14**, the sample size is jointly determined by trends in both the primary effectiveness and safety endpoints, but it is conservatively assumed that the safety objective would always pass its non-inferiority condition once enrollment had stopped. Enrollment followed the Expected rate, as described in Section 15.7.

Table 15 Type I Error Rates for Effectiveness Superiority (when $P_T = P_C = 0.65$), as data generation methods vary

Data Generation Method	Control Group			
	Treatment Group	Eff_1	Eff_2	Eff_3
Eff_1		0.0254	0.0226	0.0278
Eff_2		0.0248	0.0224	0.0225
Eff_3		0.0232	0.0238	0.0268

All estimates are based on 10,000 simulated trials (per scenario).

In **Table 15**, the maximum value is 0.0278. In **Table 15** (as well as **Table 13** and **Table 14**), no estimated type I error rates exceed the range of what is expected in a simulation of 10,000 iterations, calculated as a 95% probability interval $0.025 \pm 1.96 \times \sqrt{(0.025 \times 0.975 / 10000)} = 0.025 \pm 0.0031$, with upper bound 0.0281. Therefore, the type I error rate of the secondary effectiveness superiority test is considered controlled at the (one-sided) level 0.025.

16 Planned Sensitivity Analyses

16.1 Missing Data and Planned Sensitivity Analyses (Primary Objectives)

16.1.1 Sensitivity to Missing Data

Every effort will be undertaken to minimize missing data. However, some missingness is inevitable, and the simulations were conducted with the expectation that there may be up to 5% missing data for the primary safety analysis and 7.5% missing data for the primary effectiveness analysis. The reasons for missing data will be described in detail and evaluated for assessment of possible bias. The distribution of prognostic factors between subjects with data and those without data will be examined to evaluate any potential sources of bias.

By design, the analysis of the primary objectives will predict 12-month outcomes for any subjects without measured 12-month outcomes, based on available follow-up. At the final analysis, several additional analyses are planned that will explore the sensitivity of the main results to these predictions. Specifically:

- One analysis will exclude subjects known to be lost to follow-up without an event (or with final effectiveness outcome permanently missing). This is a completers-only analysis.
- A tipping point analysis will be conducted. This analysis will systematically consider each subject who is lost to follow-up (or has final effectiveness outcome permanently missing) as an Event or a Non-Event at 12 months, in all combinations. Posterior probabilities of non-inferiority (or superiority, as appropriate) for each combination will be presented.

16.1.2 Sensitivity to Imputation Model

In the principal effectiveness analysis, subjects without complete data will have their final outcomes imputed via the posterior predictive piecewise exponential model described in Section 13. Sensitivity to the piecewise exponential model (with 5 pieces) will be studied by instead implementing a piecewise exponential model with 6 pieces, partitioning the time axis beyond 90 days into 5 pieces with approximately equal numbers of events. Because the number and timing of events could differ between treatment arms, the partitions may be different in the two arms. As with the principal analysis, each interval of the partition will have an associated λ parameter that will be assigned a $\text{Gamma}(0.5, 0.001)$ prior, and subjects with incomplete data will have their final outcomes imputed according to this model.

16.2 Sensitivity to COVID-19

The COVID-19 pandemic has the potential to affect both the primary effectiveness and primary safety endpoints. Therefore, several sensitivity analyses are planned for handling data from subjects with documented COVID-19. At a minimum, these will be conducted for the analyses of the primary endpoints.

1. Subjects with Severe COVID-19 (defined clinically at Protocol Section 6.3.16) will be censored as of the Onset Date of their COVID-19 infection.
2. Subjects with Severe COVID-19 will be censored as of the Onset Date of their COVID-19 infection, with the exception that primary safety events that are adjudicated to be

related to device or procedure will still be included in the analysis, regardless of the date of onset of COVID-19 infection.

3. A tipping point analysis will be conducted. This analysis will systematically consider each subject who has a primary endpoint event subsequent to the Onset Date of documented severe COVID-19 as an Event or a Non-Event at 12 months, in all combinations, while all other subjects will be analyzed according to the model of Section 13. Posterior probabilities of non-inferiority (or superiority, as appropriate) for each combination will be presented.

16.3 Other Sensitivity Analyses

- A sensitivity analysis of the Primary Effectiveness Endpoint will also be conducted, in which subjects requiring ablation for an accessory pathway, AVNRT, treatment-emergent left AFL, or incessant AT are counted as treatment failures.
- As indicated in Section 9, the primary analysis for effectiveness will be conducted in the mITT population, but supportive analyses will also be conducted in the PP population. Similarly, as indicated in Section 10, the primary analysis for safety will be conducted in the Safety Population, supportive analyses will also be conducted in the PP population.
- For the primary effectiveness endpoint, Kaplan-Meier estimates of event rates will also be presented.

17 Heterogeneity/Poolability

Incidence of the primary safety and primary effectiveness endpoints will be evaluated for poolability across key subgroups. In particular, the primary endpoints will be examined for differences between sexes and sites. A specific categorization of sites is those that use RF as the control therapy and those that use cryoablation as the control therapy. Poolability of treatment effect over this factor (site uses RF, site uses cryo) will also be studied.

Poolability tests will be conducted with frequentist methods. For each factor of interest (sex, site), a logistic regression will be fit, with predictors Treatment Group, the factor, and their interaction. If the interaction p-value is significant at the level 0.15, further analyses will be conducted. At a minimum, any baseline variables found to differ between treatment groups and any baseline variables found to significantly predict a primary event (Treatment Response, or occurrence of CSE) in univariate analyses will be candidates for inclusion in logistic regression adjustment to see whether the apparent heterogeneity is explained by these factors. If so, analyses that adjust for these factors will be presented. If not, further analyses will be conducted, including presenting results separately by sex / site.

Sites with fewer than 8 subjects will be considered small sites. Poolability analyses will be summarized descriptively for all sites, but inferential tests of poolability across sites will exclude small sites. If there are many small sites, or many sites with 0 events, inferential tests of poolability across sites may not be conducted.

18 Other Planned Analyses

18.1 Assessment of Subject Blinding

Subjects will complete a survey regarding their opinion as to which study group they were assigned to at the time of discharge and at the 12-month assessment. Self-assessment of treatment status will be formally assessed according to the procedures defined by Bang et al (2004)⁷ and James et al (1996)⁸.

18.2 Roll-in Subjects

Roll-in Subjects will be summarized with descriptive statistics and will be analyzed separately from any populations composed of randomized subjects.

18.3 Adverse Events

Adverse Events will be tabulated by treatment group, by time, by seriousness, and by relatedness to device and/or procedure. Relatedness to COVID-19 will also be reported.

18.4 Procedural Assessments

Procedural Assessments are identified in Protocol Section 7.7. These will be summarized with descriptive statistics and may be summarized with either Bayesian or frequentist inferential methods. Any p-values or posterior probabilities will be nominal and not adjusted for multiplicity.

18.5 Quality of Life Assessments

Quality of Life Assessments are identified in Protocol Section 7.8. These will be summarized with descriptive statistics and may be summarized with either Bayesian or frequentist inferential methods. Any p-values or posterior probabilities will be nominal and not adjusted for multiplicity.

19 Analysis Methods for Secondary and Additional Endpoints

This section describes methods intended to be used for the Additional Endpoints (Sections 9.3 and 10.3) or other two-sample analyses, such as baseline demographic comparisons. These are Bayesian analogs to common frequentist statistical procedures (*t*-test, Wilcoxon rank sum test, chi-squared or Fisher's exact test, and an extension to the latter that includes multiple imputation similar to that employed in the analyses of the co-primary objectives).

19.1 Continuous Data: Bayesian version of a *t*-test.

Assuming that the quantity of interest Y follows a $N(\mu, \sigma^2)$ distribution, and placing a uniform prior distribution on $(\mu, \log(\sigma))$, the posterior distribution of μ has the form⁶

$$\left[\frac{\mu - \bar{y}}{s/\sqrt{n}} \middle| Y \right] \sim t_{n-1}$$

Employing this for both μ_t and μ_c , credible intervals for μ_t and μ_c can be individually calculated as the 2.5th and 97.5th percentiles from their respective (scaled t) posterior distributions. The posterior mean of the difference $\mu_t - \mu_c$ is simply the difference in means of the respective scaled- t posterior distributions, which is the difference in sample means. The distribution of the difference $\mu_t - \mu_c$ can be easily estimated by any of the following approaches:

Full Monte Carlo Sampling

Employing the above for both μ_t and μ_c , the distribution of $(\mu_t - \mu_c)$ can be estimated in Monte Carlo fashion by drawing a large number of observations (eg., 100,000) from a t_{n-1} distribution for $n = n_t$ and $n = n_c$, back-transforming these observations to the μ_t - and μ_c -scales, and subtracting the sample values. The posterior probability $P(\mu_t - \mu_c > \delta | \text{data})$ is estimated as the proportion of observed values of $(\mu_t - \mu_c)$ that exceed δ . A 95% equal-tail Bayesian credible interval (BCI) can be calculated from the 2.5th and 97.5th percentiles of the sampled distribution of $\mu_t - \mu_c$.

Monte Carlo Sampling and Integration: More precise estimates can be achieved by sampling from only one posterior distribution (say, for μ_c). The cumulative distribution function F_{T-C} of the difference $\mu_t - \mu_c$ can be written as

$$\begin{aligned} F_{T-C}(\delta) &= P(\mu_t - \mu_c \leq \delta) = P(\mu_t \leq \mu_c + \delta) = \int P(\mu_t \leq \mu_c + \delta | \mu_c) \times f(\mu_c) d\mu_c \\ &= \int F_T(\mu_c + \delta | \mu_c) f(\mu_c) d\mu_c, \end{aligned}$$

where $f(\mu_c)$ represents the density of μ_c and F_T represents the c.d.f. of μ_t .

By Monte Carlo Integration, the last integral above is approximated by $1/M \sum F_T(\mu_c + \delta | \mu_c)$ after first drawing and conditioning on a large number M (e.g., $M=100,000$) of observations from the scaled t posterior distribution for $f(\mu_c)$. The resulting quantity is a mixture of M (scaled- t distributed) cumulative distribution functions for μ_t (conditional on the sampled μ_c values). Posterior quantities such as $P(\mu_t - \mu_c < 0)$ can be easily calculated from $F_{T-C}(0)$. Quantiles of the distribution of $\mu_t - \mu_c$ can be easily computed by setting the desired quantile equal to $F_{T-C}(\delta) = 1/M \sum F_T(\mu_c + \delta | \mu_c)$ and using a numeric root-finder to solve for δ . In this manner the posterior median and a 95% BCI (calculated from the 0.025 and 0.975 quantiles) are found.

Numerical Integration: Nearly exact estimates can be achieved as follows: The cumulative distribution function F_{T-C} of the difference $\mu_t - \mu_c$ can be written as

$$\begin{aligned} F_{T-C}(\delta) &= P(\mu_t - \mu_c \leq \delta) = P(\mu_t \leq \mu_c + \delta) = \int P(\mu_t \leq \mu_c + \delta | \mu_c) \times f(\mu_c) d\mu_c \\ &= \int F_T(\mu_c + \delta | \mu_c) f(\mu_c) d\mu_c, \end{aligned}$$

where $f(\mu_c)$ represents the density of μ_c and F_T represents the c.d.f. of μ_t .

For any given value of δ , $F_{T-C}(\delta)$ can be computed by one-dimensional numerical integration, and posterior quantities such as $P(\mu_t - \mu_c < 0)$ can be easily calculated as $F_{T-C}(0)$. Quantiles of the distribution of $\mu_t - \mu_c$ can be easily computed by setting the desired quantile equal to $F_{T-C}(\delta)$ and using a numeric root-finder to solve for δ . In this manner the posterior median and a 95% BCI (calculated from the 0.025 and 0.975 quantiles) are found. This approach does not require any Monte Carlo sampling.

The above 3 methods do not require large sample sizes.

Normal Approximation

For large sample sizes, the t -distribution is well approximated by a Normal distribution, and the difference of two t -distributions is thus the difference of 2 Normal distributions, which is Normally distributed.

More specifically, approximating a t_{n-1} distribution by a Normal distribution with the same mean and variance,

$$\left[\frac{\mu - \bar{x}}{s/\sqrt{n}} \right] \sim t_{n-1} \approx N \left(0, \frac{n-1}{n-3} \right),$$

and thus $(\mu_T - \mu_C)$ is approximated by a Normal distribution with mean $(\bar{x}_T - \bar{x}_C)$ and variance $\left(\frac{(n_T-1)s_T^2}{n_T(n_T-3)} + \frac{(n_C-1)s_C^2}{n_C(n_C-3)} \right)$. Posterior probabilities and quantiles for $(\mu_T - \mu_C)$ can then be computed from this Normal distribution.

Unless otherwise specified, all implementations of this Bayesian t-test will use the (exact) Numerical Integration approach, above. Specifically, the test of PV Dimensional Change: Aggregate PV Cross-Sectional Area (Section 10.2.1) will use the Numerical Integration approach.

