## 7.8 Quality of Life Assessments

Quality of Life (QoL) will be assessed at baseline and 12 months using two assessments. These assessments will be tested for nominal p values between Pulsed Field Subjects and Thermal Subjects:

1. The EuroQol standardized questionnaire of health states (EQ-5D-3 L) at baseline and 12 months (The EuroQol Group. EuroQol - a new facility for the measurement of health-related quality of life. *Health Policy* 1990;16:199-209)
2. Atrial Fibrillation Effect on Quality of Life (AFEQT) at baseline and 12 months (Spertus J, Dorian P, Bubien R, et al. Development and validation of the Atrial Fibrillation Effect on QualiTy-of-LIfe (AFEQT) Questionnaire in patients with atrial fibrillation. *Circ Arrhythm Electrophysiol* 2011;4:15-25)

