19.2 Continuous Data (Distribution-free): Bayesian Version of a Wilcoxon Rank-Sum Test

For this test, data are ranked. Analogous to the Wilcoxon Rank-Sum test, observations in each group are replaced by their ranks in the combined order statistic. Then the two groups of rank-transformed data are compared via the Bayesian version of a t-test, above. It has been shown that conducting a two-sample t-test on rank-transformed data is approximately equivalent to the Wilcoxon Rank-Sum test^{4,5}.

Non-inferiority can be evaluated by first subtracting a margin (δ) from each observation in one treatment group prior to the rank transformation..

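### The between-arm comparison of AFEQT and EQ-5D-3L has no fixed outcome form or model, and the continuous methods the SAP writes out make no use of the baseline score

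*SAP*

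**What the plan says.** Protocol 7.8 fixes the measurement times: "Quality of Life (QoL) will be assessed at baseline and 12 months using two assessments". It also commits to a comparison: "These assessments will be tested for nominal p values between Pulsed Field Subjects and Thermal Subjects".

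SAP 18.5 is looser: "These will be summarized with descriptive statistics and may be summarized with either Bayesian or frequentist inferential methods". It adds: "Any p-values or posterior probabilities will be nominal and not adjusted for multiplicity". It gives no outcome form, model or covariate.

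The SAP's two-sample methods are in Section 19, which opens: "This section describes methods intended to be used for the Additional Endpoints (Sections 9.3 and 10.3) or other two-sample analyses". Two of them are for continuous data:

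- **19.1, Bayesian t-test.** The posterior mean of the arm difference is described as the quantity "which is the difference in sample means". There is no covariate.
- **19.2, rank version.** "Then the two groups of rank-transformed data are compared via the Bayesian version of a t-test, above". Again there is no covariate.

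SAP 7.1 is the provision that might bring in a baseline value. It makes a variable only a possible covariate, only after a significant difference between arms has been found, and only for safety or effectiveness analyses. Quality of life is not named.

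Elsewhere the SAP does fix the outcome form. Aggregate PV area (10.2.1) is 3 months minus baseline, and AF symptom counts (9.3.14) are to be given at each time point and as change.

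**The concern.** Each instrument has a baseline value, which usually predicts part of the 12-month value. A comparison that ignores it carries variance that could be removed at no cost in data collection. A raw change score removes too much of the baseline when the correlation is below 1 and the spread is similar at the two visits.

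The open choice of outcome form matters as well. The 12-month-score difference and the change difference differ by exactly the observed baseline difference between arms, so one dataset can give two answers, and nothing in the SAP says which is the planned one. These are subject-reported outcomes in a trial that tries to keep subjects unaware of their treatment (Protocol 5.7), so a single efficient analysis fixed in advance is worth having, even for a nominal result.

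**Working it through.** **Inputs.** From the documents: two instruments, each at baseline and 12 months (Protocol 7.8); 1:1 allocation (Protocol 9.2); 350 to 750 MITT subjects, or 175 to 375 per arm (SAP 12). The documents give no standard deviation, effect size, power or baseline-to-12-month correlation for either instrument, so there is no plan figure to reproduce. Assumed: a continuous score, equal standard deviation at both visits, and correlation ρ of 0.3 to 0.7.

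**Precision.** With n per arm, the variance of the arm difference in units of 2σ²/n is, in large samples:

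- 12-month score alone: 1
- change from baseline: 2(1 − ρ)
- 12-month score adjusted for baseline: 1 − ρ²

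| ρ | Score | Change | Adjusted | Saving against score | Saving against change |
|---|---|---|---|---|---|
| 0.3 | 1 | 1.40 | 0.91 | 9% | 35% |
| 0.4 | 1 | 1.20 | 0.84 | 16% | 30% |
| 0.5 | 1 | 1.00 | 0.75 | 25% | 25% |
| 0.6 | 1 | 0.80 | 0.64 | 36% | 20% |
| 0.7 | 1 | 0.60 | 0.51 | 49% | 15% |

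At ρ = 0.5 an unadjusted test needs 1/0.75 = 1.33 times the subjects for the same precision. A simulation at ρ = 0.5 with 225 per arm and 10,000 runs gave variance ratios of 0.76 (adjusted to score) and 0.75 (adjusted to change).

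**Power, as an illustration.** Take a contrast with 80% power unadjusted at two-sided 0.05. Power after adjustment is Φ(2.80 × √(V unadjusted / V adjusted) − 1.96).

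- ρ = 0.5: √(1/0.75) = 1.155, giving 89.9% against either form.
- ρ = 0.3: 83.6% starting from the score, 93.5% starting from change.
- ρ = 0.7: 97.5% starting from the score, 86.0% starting from change.

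**Effect of the equal-spread assumption.** Let the 12-month SD be k times the baseline SD. The adjusted variance is then k²(1 − ρ²), the score variance k² and the change variance 1 + k² − 2ρk. The saving against the score is still ρ². The saving against change moves. At ρ = 0.5:

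- k = 0.7: 1 − 0.3675/0.79 = 53%
- k = 1.3: 1 − 1.2675/1.39 = 9%

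It is never negative in large samples, because change minus adjusted equals (1 − ρk)².

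**Chance baseline difference.** Its standard error is √(2/n) in SD units. The 95% range is ±0.21 SD at 350 subjects, ±0.185 at 450 and ±0.14 at 750. A baseline difference d shifts the 12-month-score estimate by ρd and the change estimate by (ρ − 1)d. At ρ = 0.5 these are +0.5d and −0.5d: up to about 0.105, 0.09 and 0.07 SD at the three sizes, in opposite directions. The simulated slopes on d were +0.49 (score), −0.51 (change) and −0.01 (adjusted).

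**The case against.** The strongest reply is that SAP 18.5 does not send quality of life to Section 19. That section covers the Additional Endpoints of 9.3 and 10.3, and quality of life is reached only through its general phrase, "or other two-sample analyses, such as baseline demographic comparisons". Section 18.5 allows Bayesian or frequentist methods, so a baseline-adjusted model would comply as written. This stands. A reader might infer that the SAP prescribes an unadjusted comparison, but the text does not support that. The loss arises only if the written-out methods are used.

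Three further points also stand.

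- The 25% figure rests on an assumed correlation and, against change, on equal spread at the two visits. Neither is in the documents.
- A reader might infer that the unadjusted comparison is biased. Under 1:1 randomisation stratified by site it is unbiased on average. The issue is precision, and the error in the particular trial when baselines happen to differ.
- Quality of life is outside the multiplicity plan in SAP 6. SAP 18.4 treats procedural assessments in the same words, so the brevity looks like a consistent level of detail for supportive results.

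These points limit the concern but do not remove it. Being permitted is not the same as being pre-specified. SAP 7.1 does not fill the gap, since its trigger depends on the data and its scope is safety and effectiveness. The protocol's commitment to test is also firmer than the SAP's permission to summarise.

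**Conclusion.** The point holds as a gap in pre-specification with an easy gain in precision. No outcome form and no adjusted model are fixed for quality of life, and both continuous methods that the SAP writes out ignore baseline.

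For a continuous score with equal spread at both visits and ρ between 0.3 and 0.7, adjustment would remove 9% to 49% of the variance of the 12-month-score comparison and 35% to 15% of that of the change comparison. The direction does not depend on the assumed values in large samples; the size does. If EQ-5D-3L were analysed by dimension and not as a continuous score, these figures would not apply to it.

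It would be wrong to conclude that the trial's success or error control is at risk. These comparisons are nominal and gate nothing. The consequence is confined to how precise and how clear a supportive result is, so this is a worthwhile improvement and not a serious fault.

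**What to change.** In SAP 18.5, state that the between-arm comparison for each continuous quality-of-life score analysed is a linear model of the 12-month score on randomised arm and the baseline value of the same score, with flat priors as in 19.1. Report the adjusted difference, its 95% Bayesian credible interval and the nominal posterior probability. Keep mean change by arm as description.

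The same paragraph should say which score or scores are analysed for each instrument and how a missing baseline or 12-month value is handled, since the model needs both. It should also say that the comparison will be done, to agree with Protocol 7.8. If there is concern about distributional shape, the rank method of 19.2 can stay as a supportive check.

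The cost is SAP wording. Both values are already collected, and no threshold, sample size or testing order changes.
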